6.0 Recruitment Methods

LOCAL:

- 6.1 This study will start with the retrospective phase which does not involve recruitment of patients, but involves analysis of existing data. De-identified data will be obtained from Cigna-Healthspring.
- 6.2 The project will be implemented in collaboration with Cigna-Health Spring, a Medicare Advantage Plan in Texas. The health plan has several electronic data files available for analysis including membership file, member

A motivational interviewing intervention customized by patient adherence patterns (NCT03985098) – 03.28.2018

summary file, institutional claims file, professional claims file, quest lab, Cigna-Health Spring's medical claims file (CCMS) and pharmacy file. Pharmacy files contain Part D pharmacy data provided by pharmacy benefits manager including patient/ drug identifying information, fill dates, days of supply, quantity dispensed and dosing for each prescription filled. The refill data will be used to determine the non-adherent patients. ICD-10 codes will be used to determine other exclusions using professional claims data.

Phase 2 will involve project intervention which will be conducted over the phone. A list of actively enrolled members, taking the medication who were a part of phase 1 will be created by Cigna HealthSpring to be used for intervention implementation at their premises. The phone call will be made by University of Houston pharmacy students who will be on rotation at Cigna-HealthSpring. The form of informed consent which will be read to the patient is attached to the IRB. If the patient consents to receive the intervention over the phone, and completes the phone call, the patient forms a part of the intervention group. Five follow-up phones will be attempted one month apart for the patient after the initial call.

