8.0 Study Endpoints

- 8.1 Develop group-based trajectory models to identify patients with similar medication filling behavior patterns among patients utilizing ACEI/ARBs with co-morbid HTN and DM enrolled in a MAP and examine predictors associated with having different trajectories.
- 8.2 Customize a pharmacy student telephone intervention incorporating MI by patient adherence behavior patterns identified under aim 1.
- 8.3 Demonstrate the benefit of the customized intervention on ACEI/ARB adherence among non-adherent patients with co-morbid HTN and DM enrolled in a MAP.

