20.0 Data Management

- 20.1 The data which will be provided by Cigna will contain data with encrypted patient IDs. The electronic data files for this study will be processed on a dedicated, layered-security server, which can be accessed only by [name] and designated project staff members who are under the direct supervision of [name]. Since the system is behind multiple firewalls, is monitored regularly, and is accessible only to key personnel, the risk of unlawful penetration is not a significant data safeguard concern. Data will be stored on the secure server for 3 years following the completion of the study. All analysis will be conducted on the desktop at UH College of Pharmacy. The data will not be accessible through any personal computers.

SAS 9.4 is the statistical software, which will be used for the analysis.

A motivational interviewing intervention customized by patient adherence patterns (NCT03985098) – 03.28.2018

Baseline characteristics: Comparisons in baseline characteristics will be made between the 2 study groups (intervention vs. control) using t-tests for continuous variables and chi-square tests for categorical variables. The characteristics evaluated will include predisposing factors: demographics, and number of other medications used; enabling factors: health plan (LIS vs. not), prescriber specialty (specialist vs. primary care); need factors: comorbidities (CHF, MI, CAD, stroke, ESRD, depression), previous hospitalization and CMS risk score.

Baseline PDC in the 12 months prior to intervention and patient past adherence trajectory will also be compared between 2 groups. Because of the randomization, we do not anticipate any significant differences between the two study groups on these characteristics.

Outcome analysis: Refill data during 2 time periods -- 6, and 12 months, following the initial call of the intervention will be evaluated to calculate adherence rates for both the intervention and control groups. The two periods were chosen to evaluate the intervention effect during the 6 months when the follow up calls were ongoing as well as after these calls had stopped. The adherence rate will be defined as proportion of days covered (PDC) for six and twelve month follow up period following the intervention. An intent to treat analysis will be utilized.

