To examine the effect of study group (intervention vs. control) on adherence, study group PDC means for each follow up time, 6 and 12 months, post intervention will be calculated and compared using a t-test. In the event that significant differences in baseline characteristics were observed, multiple regression will be utilized to adjust for the imbalance. The outcome variable will be PDC during each follow up period, 6 and 12 months, following the intervention initial call. The primary exposure variable will be study group, and other covariates will include any baseline characteristics not equally distributed.

Dichotomization of the outcome: Patients in both groups will also be categorized as adherent vs. not during the two follow up periods based on PDC \geq 80% in each time period, 6 and 12 months, to create 2 categorical outcome variables. The effect of study group on adherence will be evaluated for these categorical outcomes using chi-square tests. If significant differences in baseline characteristics were observed, logistic regression models will be utilized to adjust for imbalances

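### Objective 8.3 rests on four unranked tests with no stated primary outcome, lead time point, alpha or success rule; if any one favourable result counted, the false benefit rate would be about 3-4% (two mean-PDC tests) or 5-7.5% (all four) instead of 2.5%

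*Combined protocol and SAP*

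**What the plan says.** Study Endpoints 8.3 sets one confirmatory aim for phase 2: "Demonstrate the benefit of the customized intervention on ACEI/ARB adherence among non-adherent patients". It names no measure and no time point.

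Section 20.0 (Data Management), Outcome analysis, uses "Refill data during 2 time periods -- 6, and 12 months, following the initial call of the intervention". For mean PDC, "study group PDC means for each follow up time, 6 and 12 months, post intervention will be calculated and compared using a t-test". The paragraph on dichotomization then classifies patients by PDC of at least 80% at both times: "The effect of study group on adherence will be evaluated for these categorical outcomes using chi-square tests". That makes four between-group tests.

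On the model, section 20.0 says: "In the event that significant differences in baseline characteristics were observed, multiple regression will be utilized to adjust for the imbalance". The covariates are whichever characteristics turn out unbalanced, and the same rule leads from chi-square to logistic regression for the 80% outcomes.

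The word primary is applied in section 20.0 only to the exposure variable, study group. No significance level, sidedness, test order, multiplicity rule or success criterion appears in the documents as supplied.

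**The concern.** The four results can disagree. Mean PDC may be significant while the 80% cut-off is not, or 6 months may be significant while 12 months is not. An unadjusted and an adjusted analysis may also differ. Nothing in the plan says which result then decides objective 8.3. If the choice is left until the data are in, the intervention has several chances to succeed, and the probability of claiming a benefit that does not exist exceeds that of a single test.

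Two further points leave the deciding result open. The 12-month window is justified by a wish to see "the 6 months when the follow up calls were ongoing as well as after these calls had stopped", which could be taken to mean months 7-12 and not months 1-12. The adjustment covariates also depend on which baseline tests happen to be significant.

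**Working it through.** **Inputs from the documents.** Four tests (20.0); 250-300 patients per arm with one control each (5.2); a directional hypothesis of benefit (1.2). The plan gives no alpha, power, effect size or sample-size calculation, so there is no figure of its own to reproduce.

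**Assumptions, not in the documents.** Each test two-sided 5%, so 2.5% in the favourable direction; no true effect; comparable arms; any one favourable significant result read as benefit; half-year PDC with mean 0.45-0.70 and SD 0.25-0.30; correlation r between the two half-years of 0.3-0.9.

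**Step 1, ceilings.** If the tests were independent: two tests, 1 - 0.975^2 = 4.9%; four tests, 1 - 0.975^4 = 9.6%. The tests are strongly correlated, so the true figures are lower.

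**Step 2, two mean-PDC tests.** If 12-month PDC is the average of two half-years with equal SD, its correlation with 6-month PDC is sqrt((1 + r)/2). For r = 0.3 this is sqrt(0.65) = 0.81; for r = 0.9 it is sqrt(0.95) = 0.97. The chance that at least one of two standard normal statistics exceeds 1.96 is about 3.9% at correlation 0.80 and 3.1% at 0.97.

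**Step 3, all four tests.** Null simulation with beta-distributed PDC, 30,000 trials in each of 36 settings, 250 or 300 per arm, 10-51% of patients at PDC of at least 80% over 6 months, pooled t-tests and uncorrected chi-square tests. False benefit rate:

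| Meaning of 12 months | Two mean-PDC tests | All four tests |
|---|---|---|
| Cumulative, months 1-12 | 3.0-4.1% | 5.2-7.5% |
| Months 7-12 | 3.5-4.9% | 5.8-8.5% |

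The single 6-month mean-PDC test gave 2.4-2.6%. A separate calculation over a wider range (r from 0.1 to 0.95, about 9-50% adherent) gave 2.9-4.1% and 4.8-7.7% for the cumulative window, and 3.2-4.9% and 5.4-8.5% for months 7-12.

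**Step 4, covariates chosen by baseline tests.** Section 20.0 lists about 16 comparisons: demographics (three items, as in 9.2), number of other medications, health plan, prescriber specialty, six comorbidities, previous hospitalization, CMS risk score, baseline PDC and past trajectory. At 5% each and independent, the chance of at least one significant difference with comparable arms is 1 - 0.95^16 = 56%. With 14 items, allowing for two partly balanced by randomization within trajectory, it is 1 - 0.95^14 = 51%. With correlations of 0.1-0.3 among items it is 44-55%. A two-stage null simulation (8,000 trials, 275 per arm, 15 covariates, baseline PDC correlated 0.5 with outcome and the others 0.1) used regression in 53% of trials. False benefit was 2.1%, against 2.5% for the t-test alone, and the two analyses disagreed on significance in 2.1% of trials.

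**Step 5, power of the possible primary tests.** Assumed gain of 0.07 in the first half-year, kept (0.07) or halved (0.035) in the second; SD 0.29; 275 per arm. Power is Phi(gain/SE - 1.96), with SE = 0.29 x sqrt(2/275) = 0.0247 for a half-year mean.

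- 6 months: 0.07/0.0247 = 2.83; Phi(0.87) = 81% (simulation 80-81%).
- 6 months, adjusted for a baseline PDC correlated 0.5 with outcome (assumed): SE = 0.0247 x sqrt(1 - 0.25) = 0.0214; 0.07/0.0214 = 3.27; Phi(1.31) = 90%.
- Cumulative 12 months, best case (gain kept, r = 0.3): SE = 0.0247 x sqrt(0.65) = 0.0199; 0.07/0.0199 = 3.51; Phi(1.55) = 94%.
- Cumulative 12 months, worst case (gain halved, r = 0.9): average gain 0.0525; SE = 0.0247 x sqrt(0.95) = 0.0241; 2.18; Phi(0.22) = 59%.
- Months 7-12: gain 0.035 gives 1.42 and Phi(-0.54) = 29%; gain 0.07 gives 81%.

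In simulation under the same assumptions, the chance of a claim is 81-95% if either mean-PDC test counts and 86-97% if any of the four counts.

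**The case against.** The strongest reply is that the plan does lean one way. Mean PDC comes first, the regression text says "The outcome variable will be PDC during each follow up period, 6 and 12 months, following the intervention initial call", and the 80% classification is introduced afterwards as an addition. This stands: the two-test figure is the fairer one. It does not close the gap, because 6 and 12 months are treated alike throughout.

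A reader might infer that the plan declares success on any one significant result, so that this trial's error rate is 5-8% or even the 9.6% ceiling. The documents state no such rule; they only fail to exclude it. The ceiling also ignores the correlation between the tests.

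A reader might infer that the second window is months 7-12. That is the less natural reading. Sections 2.1 and 20.0 describe periods of 6 and 12 months after the intervention, and a cumulative 12-month window also extends past the calls. One sentence should settle it.

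A reader might infer that the baseline-test rule inflates the error. It did not in the check above, and it is at least written as an if-then rule. What remains is that chance would change the analysis in about half of trials with comparable arms, and that precision is given up in the rest. Section 9.2 does list baseline PDC and prior trajectory among model covariates, but section 20.0 limits outcome adjustment to unbalanced characteristics.

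Finally, the trial is registered and the registry record was not available here. The finding is that these documents name no primary outcome, not that none exists anywhere.

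**Conclusion.** The concern holds as a gap in the documents, and that part needs no simulation: one benefit objective, four tests, and nothing that says which one decides.

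The size is modest and conditional. On the assumptions listed in the working, the false benefit rate rises from 2.5% to about 3-4% for the two mean-PDC tests. It rises to about 5-7.5% if the 80% tests count equally (cumulative window), and to at most about 8.5% under the months 7-12 reading. Confidence is high on the missing specification and lower on the magnitudes, since alpha, success rule, PDC distribution and correlation are all assumed.

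The 2.5% baseline also presumes comparable arms. Section 6.2 says that a patient who consents "and completes the phone call, the patient forms a part of the intervention group", while 9.3 draws controls at random from those assigned to control. Whether that preserves comparability is a separate question, which this point does not settle.

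**What to change.** Before outcome data are seen, state in section 20.0:

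1. Alpha: two-sided 5%.
2. Primary outcome: mean PDC over the first 6 months from the initial call.
3. Primary analysis: linear regression of PDC on study group, with baseline PDC and phase 1 trajectory fixed in advance. Both are already collected, and randomization is within trajectory. This replaces covariates selected by baseline tests.
4. Mean PDC over 12 months, with the window stated as cumulative, tested only if the primary test is significant.
5. Both comparisons of PDC of at least 80% reported as supportive, with confidence intervals.

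The cost is wording only, with no extra patients or data. The downside is that a lone significant non-primary result no longer carries the claim. Part of the higher chance of a claim under the looser rules (81-95% or 86-97%) comes from allowing more attempts.

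The choice of primary window is not neutral. Under the assumed effect, unadjusted power is about 80-81% at 6 months, against 59-94% for a cumulative 12-month primary and 29-81% for months 7-12. Adjusting for baseline PDC would raise the 6-month figure to about 90% if its correlation with outcome is 0.5. The sponsor should replace these assumed values with estimates from the phase 1 refill data where it can.

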2.0 Background

2.1 Diabetes (DM) and hypertension (HTN) are independent risk factors for cardiovascular (CV) disease and major public health issues in the United States (US). The two conditions frequently coexist, with 70-80% of DM patients also having HTN. The combination significantly increases the risk of macrovascular and microvascular DM complications. Controlling high blood pressure (BP) can greatly reduce these complications including the CV risk which accounts for 50-80% of DM fatalities. Angiotensin converting enzyme inhibitors (ACE) and Angiotensin receptor blockers (ARB) are highly recommended for patients with DM and HTN, with a well-documented benefit in reducing DM complications.

The project will have 2 phases: Phase 1 will be a retrospective analysis of 12 month refill data to determine patient past adherence behavior patterns. Phase 2 will entail a prospective randomized design among non-adherent patients to evaluate the effectiveness of the customized intervention. The students will contact patients assigned to the intervention group and follow a protocol using the Ask-Provide-Ask approach of MI given the patient adherence pattern for a tailored education. Monthly follow-up calls for 6 months will be carried out. Adherence during the 6 and 12 months post-intervention, will be evaluated for the intervention and control groups.

Findings are expected to demonstrate the effectiveness of an innovative low cost intervention in improving adherence and have a positive impact in implementing tailored interventions leading to more desirable long term health outcomes and considerable cost savings in our financially overwhelmed healthcare system.

2.2 The primary investigator has conducted prior research collaborating with Cigna Healthspring using motivational interviewing techniques over phone calls. The IRB reference of the last study is: 16410-01-(7926)

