4.0 Vulnerable Populations

4.1 N/A

5.0 Number of Subjects

- 5.1 This study will have two phases. In the retrospective analysis stage, Cigna Healthspring will provide data on patients who fulfill eligibility criteria mentioned above. It is expected that this data will have approximately 22,000 patients with DM and HTN.
- 5.2 In the intervention phase, 250-300 patients will be included in the intervention phase. If 1 control is used for each patient in the intervention group, the total sample of phase 2 is expected to be 500-600.

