Customization of intervention: After completion of the retrospective analysis phase and identifying the major trajectories in this patient population, the team will meet to discuss the patterns identified, the potential barriers likely to be associated with each trajectory, and strategies that can help patients within each trajectory based on their behavior pattern. The team will then develop customized education specific to each identified trajectory. For example: some patients can have high medication use in the early part of the follow up period but poor after, others may have low initial use and improved subsequent. Some may have intermittent adherence throughout the follow up time, others may simply discontinue. The expected barrier and potential solutions that should be discussed with the patient using MI strategies will vary accordingly. Patients past adherence patterns will guide the team in determining probable barriers and what can potentially help the patient. For example, patients who discontinue the medication may have side effects concerns or may view the medication as unnecessary. Patients who continue to take medication but have less than 0.8 PDC throughout may be forgetting to take the medicine and need help remembering. The team will create a code for each trajectory identified to categorize the patients. A protocol for each trajectory will be developed to summarize the education that is likely to benefit patients with the specific behavior pattern given the code. All the developed protocols will be based on the Ask-Provide-Ask approach, a pharmacist adaptation for the Elicit-Provide-Elicit approach of MI (attached)

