9.3 Phase 2: intervention implementation

Patients that are still enrolled in the health plan during 2017-2018 will be included in phase 2. Patients will be categorized by their adherence trajectory identified in phase 1 and will be randomized to intervention vs. not within each category. The proposed intervention will be a telephone call by a pharmacy student participating in rotations at Cigna-Health Spring Plan and trained in MI and 6 monthly follow up calls. During implementation, students will first examine the patient adherence pattern that was identified in phase 1 which will be coded. The student will then confirm the diagnosis, medication name, and dose with the patient answering the call and will follow the outlined protocol. Using MI, students will assess readiness for change, help patients identify potential barriers in accordance with patient past pattern of use, and guide them to develop a plan to deal with these barriers

A motivational interviewing intervention customized by patient adherence patterns (NCT03985098) – 03.28.2018

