Additionally, the students will ask the 2 questions from the Patient Health Questionnaire (PHQ)-2, a validated screening tool for depression (attached). If the patient responds positively to either question, the student will suggest that the patient schedules an appointment with his/her healthcare provider to discuss these symptoms. The Supervising pharmacists will be available to assist the students in answering any medication related questions that may arise during the calls and arrange for a diabetes educator to contact the patient at a later time if needed. Follow up phone calls will be performed each month for a total of six calls. Students will be supervised by the pharmacist preceptors and managed care pharmacy residents throughout the calls and intervention implementation. The students who will be implementing the calls will attend a three day MI training facilitated by [name], who is experienced in utilizing motivational interviewing to improve adherence. The students will practice calls as a part of their training. They will also complete Human Subjects Research training before their rotation at Cigna Healthspring, and the certificates will be uploaded to the IRB application. After each initial call, students will record the date and write a summary of the interaction with the patient documenting the main barrier/s identified in the conversation and the plan made with the patient. During the follow up calls, students will emphasize the information, confirm problem solved, provide further encouragement and reinforce adherence.

Control group: For every patient that received a call, a control will be randomly selected from the list of patients randomly assigned to the control group.

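### Education is tailored and randomisation stratified by adherence trajectory, but only pooled tests are planned, so no effect by trajectory is estimated and a benefit cannot be credited to the tailoring.

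*Combined protocol and SAP*

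**What the plan says.** Phase 1 groups patients by refill pattern. The customisation paragraph in section 9 then says: "The team will then develop customized education specific to each identified trajectory". Each trajectory gets a code and a written protocol, on the premise that barriers and solutions differ by pattern. For example, stopping the drug may reflect side-effect concerns, while persistently low coverage may reflect forgetting.

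Section 9.3 stratifies the allocation by the same variable: patients "will be randomized to intervention vs. not within each category". The comparator is no call. For each patient called, "a control will be randomly selected from the list of patients randomly assigned to the control group". No arm receives motivational interviewing (MI) calls with uniform content.

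The outcome analysis in section 20.0 is pooled: "study group PDC means for each follow up time, 6 and 12 months, post intervention will be calculated and compared using a t-test". Chi-square tests at the same two time points cover PDC of at least 80%. Regression enters only if baseline characteristics differ significantly, and then with study group plus the unbalanced characteristics.

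Trajectory appears in two other places: section 9.2 lists it among the risk-adjustment covariates, and section 20.0 compares it between groups at baseline. No effect by trajectory and no interaction is planned. Section 2.1 expects the findings to "have a positive impact in implementing tailored interventions".

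**The concern.** The trial's premise is that different filling patterns need different conversations. It builds that premise into the intervention and the randomisation, then averages over it in the analysis. A benefit in patients who forget and none in patients who stopped the drug would be reported as one intermediate number, and nobody would have said in advance how to look behind it. Estimates by trajectory produced later would be post hoc.

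The second issue is interpretation. Called patients receive MI contact, monthly follow-up, a depression screen with a prompt to see their provider, a diabetes educator if needed, and trajectory-specific content. Controls receive no call. A positive result supports the bundle. A reader who starts from the sentence on tailored interventions in section 2.1 could take it as evidence for the tailoring itself.

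**Working it through.** **Inputs from the documents.** Section 5.0: "250-300 patients will be included in the intervention phase". The control count is conditional: "If 1 control is used for each patient in the intervention group". The stated phase 2 total reproduces: 2 × 250 = 500 and 2 × 300 = 600. There is no power calculation to reproduce.

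**Assumptions.** The documents give no SD of PDC, alpha, power, or number of trajectories. I take 275 per arm (midpoint of 250 and 300), SD 0.30 with a range of 0.20 to 0.35, two-sided 0.05, no dropout, and K = 3, 4 or 5 equal trajectories with equal arms. Section 9 gives four example patterns, so 3 to 5 is plausible but not stated.

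**What the pooled test can see.** Take four equal trajectories and SD 0.30. True effects of 0.10 in all four, or of 0.20, 0.20, 0 and 0, both average 0.10. Approximate pooled power is the same for both: 96% at 250 per arm and 98% at 300. The planned test cannot separate these cases.

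**Precision.** With m = 275/K per arm in a trajectory:

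- within one trajectory, half-width = 1.96 × SD × √(2/m);
- for the difference in effect between two trajectories, half-width = 1.96 × SD × √(4/m), which is √2 times wider.

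Pooled: 1.96 × 0.30 × √(2/275) = 0.050. By trajectory, at SD 0.30:

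| K | m per arm | Half-width within | Half-width between two | Power, 0.20 contrast | Power, 0.10 contrast |
|---|---|---|---|---|---|
| 3 | 91.7 | 0.087 | 0.12 | 89% | 36% |
| 4 | 68.75 | 0.100 | 0.14 | 79% | 28% |
| 5 | 55 | 0.112 | 0.16 | 70% | 23% |

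Power = Φ(d / (SD × √(4/m)) − 1.96) for a contrast d between two given trajectories. For K = 4 and d = 0.20, the standard error is 0.30 × √(4/68.75) = 0.0724, and Φ(2.76 − 1.96) = 79%.

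**Sensitivity.** With K = 4, the within-trajectory half-width runs from 0.067 (SD 0.20) to 0.117 (SD 0.35). At SD 0.35, power for the 0.20 contrast falls to about 78%, 66% and 56% for K = 3, 4 and 5. A trajectory holding 10% of patients (27.5 per arm) has a half-width of 0.16 at SD 0.30. If the true effect is uniform and the pooled test has 80% power, power inside one of 3, 4 or 5 equal trajectories is only 37%, 29% or 24%.

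**Whether each trajectory keeps a randomised comparison.** Section 9.3 allocates within trajectory. Section 6.2, however, puts into the intervention group those who consent and complete the call, and section 9.3 draws one control per called patient without saying that the control comes from the same trajectory. Section 20.0 announces an intent-to-treat analysis. Equal and comparable arms within a trajectory, which the figures above assume, are therefore not secured as written.

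**The case against.** The strongest reply is that the planned test fits the stated aim. Sections 1.1, 1.2 and 8.3 ask whether the customised intervention improves adherence; a pooled comparison with no call addresses that. This stands. A reader might infer that the pooled test is the wrong primary analysis, or that the trial cannot meet its aim. The documents support neither.

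A reader might also infer that the trial sets out to show tailored calls beat uniform ones. It does not: the sentence in section 2.1 is a hope about impact, and no aim or test makes that comparison. What remains is a risk of over-reading, which one sentence would remove.

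Nor is trajectory absent. It is coded for each patient, listed as a covariate and checked at baseline, so the data would allow estimates by pattern. The gap is prespecification. A main-effect covariate still yields one average effect, and section 20.0 adds covariates only if they are unbalanced.

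It is also fair to say that the protocols are variants of one programme: all use Ask-Provide-Ask, the same calls and the same screen. That justifies pooling for the main result, but does not make the effect uniform.

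Finally, the strata are small. This also stands, and it sets the status of the added analyses.

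**Conclusion.** The point holds as a gap in prespecification and interpretation. The pooled comparison can in principle serve aim 8.3. As planned, it yields no estimate by trajectory, cannot distinguish a uniform benefit from one confined to some patterns, and cannot credit a benefit to customisation because no arm receives untailored calls.

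It would go too far to say that estimates by trajectory would tell the sponsor which protocols to keep. Under the assumptions above (SD 0.30, equal trajectories), a contrast as large as 0.20 between two patterns would be found with about 70% to 89% power, but one of 0.10 with only about 23% to 36%. Unequal trajectories or a larger SD make this worse. The estimates would describe heterogeneity and should not by themselves decide the fate of a protocol.

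**What to change.** In section 20.0:

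- Include the randomisation trajectory in the model for PDC at 6 and at 12 months, whether or not it looks unbalanced.
- Add, as secondary and exploratory, the intervention-minus-control difference with 95% CI within each trajectory, and a group-by-trajectory interaction. State that the trial is not powered for these.
- Compare patients as randomised within trajectory. If one control is drawn per called patient (section 9.3), draw it from the same trajectory.

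In section 2.1, state that the conclusion concerns the whole call programme against no call, and that the added value of customising over uniform MI is not tested.

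The cost is some plan wording and a few further estimates from data already held, with no new patients. The price is wide intervals by trajectory and a narrower headline claim. Testing the tailoring itself would need an untailored call arm, which is a different trial and is not asked for here.
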